11.2.2 Adverse Events of Special Interest

The Adverse Events of Special Interest (AESI) categories will be summarized and presented by treatment group and overall using primary MedDRA system organ classes

(SOCs) and preferred terms (PTs). The AESI categories will be identified by the following search criteria per Standard MedDRA Queries (SMQs)/Company MedDRA Queries (CMQs) in [Table 6](#) below.

Table 6. AESI with SMQs/CMQs/PTs Searches

AESI	Type of MedDRA Query	Broad or Narrow Search	SMQ/CMQ Search Criteria
Serious Infections	CMQ		"Infections" – Subset for SAEs
Opportunistic Infection	CMQ		"Opportunistic Infection"
Malignancy	SMQ	Narrow	"Malignancies"
Confirmed Malignancy	SMQ		"Malignant tumours"
Non-Melanoma Skin Cancer (NMSC)	SMQ	Broad	Skin Malignant tumours (Broad SMQ) removing Melanoma CMQ
Confirmed Malignancy excluding NMSC			Confirmed Malignancy Narrow SMQ and removing NMSC output
Lymphoma	SMQ		"Malignant Lymphomas"
Hepatic Disorder	SMQ	Narrow	"Drug Related Hepatic Disorders"
Gastrointestinal Perforations	SMQ	Narrow	"Gastrointestinal Perforation"
Anemia	CMQ		"Non-Hemolytic and Non-Aplastic Anemias"
Neutropenia	CMQ		"Hematological Toxicity – Neutropenia"
Lymphopenia	CMQ		"Hematological Toxicity – Lymphopenia (Veliparib Product Specific)"
Herpes Zoster	CMQ		"Herpes Zoster"
Creatine Phosphokinase (CPK) Elevation	PT		Search only for the PT of "Blood creatine phosphokinase increased"
Renal Dysfunction	SMQ	Narrow	"Acute Renal, Failure"
Tuberculosis	CMQ		"Tuberculosis"
Adjudicated Cardiovascular Events: MACE (Fatal and Non-fatal) Undetermined/Unknown Cause of Deaths Other Cardiovascular events* Venous Thromboembolic Events*,** Other Venous Thrombosis* Arterial Thromboembolic Events*	Output from CAC		

* Non-fatal events.

** Include deep vein thrombosis (DVT) and pulmonary embolism (PE).

Additional AEs may be considered for tabulation/summary based on recommendations from Clinical and Safety as deemed appropriate.

11.3 Analysis of Laboratory Data

Changes from Baseline in continuous laboratory parameters will be summarized by n, mean, standard deviation, minimum value, median, and maximum value for each treatment group. The mean change from Baseline will be compared between treatment groups and placebo at each time point using the ANOVA model with treatment as a factor. The differences between treatment groups and placebo for mean changes from Baseline will be summarized using the mean, standard error, 95% confidence interval, and *P* value for the between-group difference.

Cross (Shift) tables from Baseline to the final value according to the normal range will be provided for each hematology, clinical chemistry parameter and urinalysis parameter except for the microscopic examination.

For selected laboratory parameter with Common Toxicity Criteria (CTC) a listing of all subjects with any laboratory determinations meeting CTC Version 3.0 (or later) of Grade ≥ 3 will be provided. For hemoglobin, an additional list will also be provided based on CTC Version 3.0 (or later) of Grade ≥ 2 . For each of these subjects, the whole course of the parameter will be listed. For subjects with laboratory values with CTC ≥ 3 , all of the laboratory parameters for those subjects will be listed.

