based on the differentiated selectivity profile for JAK inhibition, upadacitinib could demonstrate an improved benefit/risk profile compared to other less selective JAK inhibitors or other therapeutic strategies for patients with inflammatory diseases.

To date, upadacitinib has been investigated in 22 Phase 1 studies with healthy volunteers (one of which also employed a substudy in subjects with mild to moderate RA), and multiple Phase 2 or Phase 3 studies for indications of RA, CD, AD, PsA and UC. Upadacitinib has been shown to be effective in the treatment of the indicated medical conditions based on the data available from the various studies. Safety results across the studies showed that upadacitinib was well tolerated and the types and frequencies of AEs were consistent with subjects with the medical conditions receiving immunomodulatory therapy. Many of the safety findings are expected for the class products with JAK inhibition, such as infections, increase in LDL-C and HDL-C, and asymptomatic and transient CPK elevation.

Upadacitinib has been evaluated in Phase 2b dose ranging placebo-controlled study in subjects with moderately to severely active UC with a history of inadequate response to or intolerant to immunosuppressants, corticosteroids or biologic therapies (Study M14-234 Substudy 1). At the time of this amendment, Phase 2b interim results from this Study M14-234 Substudy 1 Part 1 became available. The primary objective of demonstrating statistically significant dose-response relationship of upadacitinib compared to placebo for the primary endpoint and all ranked secondary endpoints was met, with the highest rates observed in the 45 mg once daily (QD) treatment group for both clinical and endoscopic endpoints. Upadacitinib was generally safe and well tolerated. No new safety concerns were identified compared to what has been observed in studies of upadacitinib in other disease indications.

A detailed discussion of the preclinical toxicology, metabolism, pharmacology and safety experience with upadacitinib can be found in the current Investigator's Brochure.²⁰

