9.3 Analysis of Laboratory Data

Data collected from central and local laboratories, including additional laboratory testing due to an SAE, will be used in all analyses, except for Baseline where SAE-related laboratory assessments on or before the first dose of study drug will be excluded. The clinical laboratory tests defined in the protocol (e.g., hematology and clinical chemistry) will be summarized.

Analysis of Quantitative Laboratory Parameters

Each laboratory variable will be summarized for all time points (starting with Baseline) with the number of non-missing observations, mean and standard deviation, median, minimum and maximum. Mean change from Baseline to each applicable post-baseline visit will be summarized for selected laboratory variables, with the number of observations, baseline mean, and visit mean. The change from baseline mean, standard error, and 95% confidence interval will be presented for the mean change from Baseline within each treatment group.

For SA1 population, treatment group differences between upadacitinib treatment group and placebo group for changes from Baseline will be analyzed using a one-way Analysis of Variance (ANOVA) model with treatment as a fixed factor and 95% CI for treatment difference will be presented for selected laboratory parameters.

Shift Table Analyses

Changes in laboratory parameters will be tabulated using shift tables categorized as low, normal, or high based on the normal ranges of the laboratory used for each sample. A shift table from Baseline to minimum and maximum value (based on normal range) will be created. A similar shift table will be provided to summarize shifts from Baseline to the final post-baseline value.

Potentially Clinically Significant Laboratory Values

The criteria for potentially clinically significant laboratory values will be determined by CTCAE criteria of Grade 3, Grade 4 and \geq Grade 3, with a grade worsening compared to baseline. Toxicity grading scale is based on National Cancer Institute Common Toxicity Criteria (NCI CTC) AE version 4.03. The number and percentage of subjects meeting the criteria for potentially clinically significant laboratory values will be summarized by treatment group. Listings will be provided to summarize subject-level laboratory data for subjects meeting the criteria.

Assessment of Liver Elevations

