Once the 250 randomized subjects have completed 8-week induction, an analysis of efficacy and safety (selected laboratory parameters) of ABT-494 versus placebo will be performed. This analysis is referred to as dose-selection analysis thereafter. Based on this planned analysis, one induction dose of ABT-494 (Dose A) will be identified for further evaluation in Substudy 2 of Protocol M14-234. In addition, the doses to be evaluated in Substudy 3 may be modified based on this analysis. The results of this analysis will be reviewed and discussed with regulatory authorities, as applicable, prior to initiation of enrollment of subjects in Substudy 2.

[figure not shown]
During the analysis period, approximately 100 additional subjects will continue to be randomized in Substudy 1 to receive one of the following treatments: 30 mg QD or 45 mg QD. There will be 50 subjects per dose group. The objectives of enrolling these additional subjects are to avoid interrupting the study activities during the analysis period and to support a sufficient number of subjects with clinical response to be re-randomized

into the maintenance portion in Substudy 3. The data collected from these subjects will be reported separately in the final clinical study report.

Subjects in Substudy 1 who do not achieve clinical response after completion of the 8-week induction treatment will have the option to enroll into a separate AbbVie Study M14-533, a Phase 3 multicenter open-label study, and receive oral ABT-494 therapy. Clinical response is defined as a decrease from baseline in the Adapted Mayo score ≥ 2 points and $\geq 30\%$ from baseline, PLUS a decrease in rectal bleeding subscore (RBS) ≥ 1 or an absolute RBS ≤ 1 .

The schematic of the study design for Substudy 1 is shown in [Figure 1](#).

Figure 1. Study Design Schematic (Substudy 1)

Study procedures can be found in Section 5.3.1.1 and Appendix C of the protocol.

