6.0 Analysis Conventions

Definition of Baseline

The Baseline visit date for Substudy 1 is the date when the first dose of study drug is received and referred to as Day 1 or Week 0. The Baseline value for a variable is defined as the last non-missing value on or before the date of the first dose of study drug.

Definition of Final Observation

Final Observation in the 8-week Substudy 1 is defined as the last non missing observation collected within 30 days following the last dose of study drug for subjects who are not re-randomized into Substudy 3 or enrolled into Study M14-533, and on or before the day of the first dose of study drug in Substudy 3 or Study M14-533 for subjects who are re-randomized into Substudy 3 or enrolled into Study M14-533. Of note, the efficacy,

laboratory, and vital sign evaluations performed on the day of the first dose of study drug in Substudy 3 or Study M14-533 for Substudy 1 subjects will be included in the efficacy and safety analyses for Substudy 1. AEs with onset on the date of the first dose of Substudy 3 or Study M14-533 will be attributed to Substudy 3 or Study M14-533, respectively.

Definition of Study Drug Exposure

Study drug exposure during Substudy 1 is measured as follows:

Study drug exposure = (date of last dose of study drug – date of first dose of study drug + 1 day).

Definition of Rx Days (Days Relative to the First Dose of Study Drug)

Rx Days are calculated for each time point of interest and it provides a quantitative measure of days between the event and the first dose date. That is, the Rx Day is calculated as the event date minus the date of first dose of study drug plus 1. The Rx Day will be a negative value when the time point of interest is prior to the date of first dose of study drug, and the Rx Day will be a positive value when the time point of interest is after the first dose date. By this calculation algorithm the first dose day is Rx Day 1, while the day prior to the date of first dose is defined as Rx Day –1 (there is no Rx Day 0). Rx Days are used to map actual study visits to the protocol specified study visits.

Definition of Analysis Windows

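### For non-hepatic laboratory tests, Substudy 1 plans no count by dose of worst post-baseline values or of Grade 3 or higher results, so transient abnormalities not reported as adverse events are not compared categorically across doses

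*SAP*

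**What the plan says.** Substudy 1 SAP, Section 11.3, plans three kinds of laboratory output:

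- **Shift tables:** "Cross (Shift) tables from Baseline to the final value according to the normal range will be provided". They cover hematology, chemistry and urinalysis, apart from urine microscopy. Section 11.1 of that SAP has safety variables summarised by treatment received, so the tables can be read as by arm.
- **Graded results:** "a listing of all subjects with any laboratory determinations meeting CTC Version 3.0 (or later) of Grade ≥ 3 will be provided". Hemoglobin gets a further listing from Grade 2. No count or percentage by arm is named.
- **Means:** "The mean change from Baseline will be compared between treatment groups and placebo at each time point using the ANOVA model with treatment as a" (last word omitted).

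Section 6.0 defines the final observation as "the last non missing observation collected within 30 days following the last dose of study drug" when the subject goes on to neither Substudy 3 nor Study M14-533. When the subject does continue, it is the last value up to the first dose in the next study.

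The Substudy 2 and 3 SAPs, in Section 9.3 of each, go further: "A shift table from Baseline to minimum and maximum value (based on normal range) will be created". That is in addition to the shift to the final value. They also tabulate by treatment group the number and percentage with CTCAE version 4.03 Grade 3, Grade 4 and Grade 3 or higher that worsened from Baseline.

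**The concern.** Substudy 1 is the trial's only dose-ranging comparison. Its SAP (Section 4.2) says that, to choose the induction dose, "an analysis of efficacy and safety (selected laboratory parameters) of ABT-494 versus placebo will be performed". A shift table that looks only at the last value cannot show an abnormality that came and went. Such abnormalities are expected: Protocol Section 3.0 names "asymptomatic and transient CPK elevation" among the class findings and describes several other laboratory changes with JAK inhibitors as reversible. Protocol Table 5 also links several low blood counts to interruption of drug until the value recovers, which makes a normal last value more likely in a subject who had the abnormality.

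If a dose raised the rate of short-lived cytopenia or CPK elevation, the planned categorical tables for those tests could look similar across arms. The graded results that would show the difference would be in listings that the SAP does not ask anyone to count.

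**Working it through.** **Step 1. Which Substudy 1 outputs can show a transient abnormality by arm?**

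- Shift table (11.3): only if the abnormality is present at the final value.
- Grade 3 or higher listing (11.3): any value qualifies, but there is no count by arm.
- Mean change (11.3): every visit and every arm against placebo, but a mean responds weakly to a few large excursions.
- Liver thresholds (11.3.1): counts and percentages by arm on post-baseline values, so transient liver elevations are covered.
- Adverse events and events of special interest (11.2.1, 11.2.2): by arm, including anemia, neutropenia, lymphopenia, CPK elevation and renal dysfunction, provided the abnormality was reported as an event.

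Protocol Section 6.1.1.1 makes a laboratory abnormality an adverse event if it leads to discontinuation, needs medical intervention, meets the Section 6.1.7 toxicity criteria, or is judged one by the investigator. What is left is the non-hepatic abnormality that meets none of these. For example, several Table 5 criteria need confirmation by a repeat test, so an unconfirmed low count need not be reported.

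**Step 2. How much can the final-value table miss?** The documents state no figure, so this is an illustration. Hematology and chemistry have four scheduled post-baseline samples: Weeks 2, 4, 6 and 8 (Substudy 1 SAP, Table 1). Assume that the final value is Week 8, that onset is equally likely at each visit, and that an abnormality lasts d visits. It is present at Week 8 if onset falls in the last d visits:

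capture = d/4

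If instead a two-visit abnormality must fit wholly inside the schedule (Weeks 2–4, 4–6 or 6–8), capture is 1/3.

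**Step 3. Effect on the comparison.** Assume a worst-value incidence of 20% on one dose and 4% on placebo. Neither rate is in the documents. Take 50 per arm (250 subjects randomised equally to five arms) and the two-sided Fisher test at 0.05 that Section 11.1 names for categorical safety variables. Final-value rate = worst-value rate × capture.

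| Duration | Capture | Rates shown | Exact power |
|---|---|---|---|
| Worst value counted | 1 | 20% v 4% | 59% |
| Three visits | 3/4 | 15% v 3% | 40% |
| Two visits | 1/2 | 10% v 2% | 19% |
| Two visits, wholly within schedule | 1/3 | 6.7% v 1.3% | 6% |
| One visit | 1/4 | 5% v 1% | 2% |

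An abnormality that persists to Week 8 loses nothing.

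**Step 4. Lipids.** The Substudy 1 SAP, Table 2, schedules fasting lipids only at Weeks 0 and 8. For them the final value is normally the only post-baseline value, so minimum and maximum shifts add little. The missing grade count still applies.

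**The case against.** A reader might infer that transient toxicity, including toxicity that led to drug interruption, disappears from the dose comparison altogether. The documents do not support that. Abnormalities meeting the Table 5 interruption criteria are adverse events under Protocol Section 6.1.1.1 and so belong in the by-arm event tables, with Fisher tests of each dose against placebo. Liver elevations are counted by arm on post-baseline values, and means are compared at every visit. One caveat: the adverse event definition is read from the current protocol, while this SAP was written to Amendment 2, which is not supplied.

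Three further objections carry weight.

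- The shift to the final value is what Protocol Section 8.1.8.3 asks for, so the SAP does not contradict it. The same section also calls for the frequency of abnormal values, however, and for non-hepatic tests Section 11.3 delivers this only at the final value.
- The 30-day window applies only to subjects who do not continue into Substudy 3 or Study M14-533. Most subjects had one of those routes open, and the 30-day contact is not a laboratory visit. For most, the final value is probably near Week 8.
- The listing covers any Grade 3 or higher result and shows the whole course of the parameter. With about 50 subjects per arm, counts could be made by hand. They would still be unplanned, and the listing has no requirement of worsening from Baseline.

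It is also tempting to say that the choice of 45 mg was distorted. Protocol Section 5.6.4 describes exposure-response modelling and laboratory effects, and nothing shows that the shift tables drove the decision.

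**Conclusion.** The gap is real but bounded. It concerns non-hepatic tests, and within them abnormalities that resolve before the last value and are not reported as adverse events. For these, Substudy 1 has no planned categorical comparison by dose, although the sponsor's own later SAPs do. The size cannot be fixed from the documents. The fall from 59% power to between 2% and 40% rests on assumed incidences of 20% and 4%, assumed durations of one to three visits and uniform onset, and it describes the shift table alone, not the safety analysis as a whole. The point is worth acting on because the change is cheap and gives a better dose comparison. It is not evidence that the dose was wrongly chosen.

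**What to change.** In Section 11.3 of the Substudy 1 SAP:

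1. Add shift tables from Baseline to the minimum and to the maximum post-baseline on-treatment value, beside the existing shift to the final value.
2. Tabulate by arm the number and percentage of subjects with Grade 3, Grade 4, and Grade 3 or higher results (for hemoglobin also Grade 2 or higher) that worsened from Baseline. Name CTCAE version 4.03, as the Substudy 2 and 3 SAPs do; the present wording permits that version but does not fix it.

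Induction in Substudy 1 is complete, so these would be supplementary tables from data already collected, in a form that the Substudy 2 and 3 SAPs already specify. The cost is a few more tables. Worst-value tables also pick up more random single abnormal values in every arm, so they must be read against placebo and not as absolute rates.

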11.3.1 Assessment of Liver Elevation

According to FDA's Guidance for Industry "Drug-Induced Liver Injury: Premarketing clinical evaluation (July 2009), when aminotransferase (AT) abnormalities indicating hepatocellular injury are accompanied by evidence of impaired hepatic function (bilirubin elevation $> 2 \times$ ULN), in the absence of evidence of biliary obstruction (i.e., significant elevation of ALP) or some other explanation of the injury (e.g., viral hepatitis, alcohol hepatitis), the combined finding (i.e., Hy's Law cases) represents a signal of a potential for the drug to cause severe DILI.

For the purpose of assessing for potential Hy's law cases, the frequencies and percentages of subjects with post baseline liver specific function test values that meet the following criteria of potential clinical interest will be summarized by treatment group:

- $ALT \geq 3 \times ULN$
- $ALT \geq 5 \times ULN$
- $ALT \geq 10 \times ULN$
- $ALT \geq 20 \times ULN$
- $AST \geq 3 \times ULN$
- $AST \geq 5 \times ULN$
- $AST \geq 10 \times ULN$
- $AST \geq 20 \times ULN$
- $TBL \geq 2 \times ULN$
- Alkaline phosphatase $\geq 1.5 \times ULN$
- ALT and/or $AST \geq 3 \times ULN$ and concurrent $TBL \geq 1.5 \times ULN$
- ALT and/or $AST \geq 3 \times ULN$ and concurrent $TBL \geq 2 \times ULN$

A listing of potentially clinically significant liver elevations based on criteria specified above will be provided. For each of these subjects, the whole course of the respective parameter will be listed.

11.4 Analysis of Vital Signs and Weight

The following vital signs are measured at every visit during the study.

- Body Weight (kg)
- Blood Pressure (Systolic/Diastolic) (mmHg)
- Pulse (bpm)
- Respiratory Rate (RPM)
- Temperature (°C)

Changes from Baseline in vital sign values will be summarized by n, mean, standard deviation, minimum value, median, and maximum value for each treatment group. The mean change from Baseline will be compared between treatment groups and placebo at each time point using the ANOVA model with treatment as a factor. The differences between treatment groups and placebo for mean changes from Baseline will be summarized using the mean, standard error, 95% confidence interval, and *P*-value for the between-group difference.

In addition, incidence of potential clinically significant results will be summarized.

The criteria for potentially clinically significant vital sign findings are presented in [Table 7](#).

Table 7. Criteria for Potentially Clinically Significant Vital Sign Findings

Vital Sign	Category	Criteria for Potential Clinically Significant Vital Signs
Systolic blood pressure	Low	Value \leq 90 mmHg and decrease \geq 20 mmHg from Baseline
	High	Value \geq 160 mmHg and increase \geq 20 mmHg from Baseline
Diastolic blood pressure	Low	Value \leq 50 mmHg and decrease \geq 15 mmHg from Baseline
	High	Value \geq 105 mmHg and increase \geq 15 mmHg from Baseline
Pulse	Low	Value \leq 50 bpm and decrease \geq 15 bpm from Baseline
	High	Value \geq 120 bpm and increase \geq 15 bpm from Baseline
Respiratory Rate	Low	< 10 rpm
	High	> 24 rpm
Body temperature	High	> 39.0°C (102.3°F)
Weight	High	> 7% increase from baseline
	Low	> 7% decrease from baseline

12.0 Summary of Changes

This is the first version of the SAP.

12.1 Summary of Changes Between the Latest Version of Protocol and the Current SAP

The statistical analyses include in this SAP reflect the latest version of protocol.

12.2 Summary of Changes Between the Previous Version and the Current Version of the SAP

This is the first version of the SAP.

